## **6.3 TREATMENT ASSIGNMENT**

This is a randomized, open-label study. After written informed consent has been obtained, all screening procedures and assessments have been completed, and eligibility has been established for a participant, the study site will obtain the participant's study identification number from the IxRS. For those participants who are eligible for randomization into the maintenance phase of the study, the study site will obtain the participant's randomization number and treatment assignment from the IxRS once eligibility has been established during the maintenance screening phase.

Participants will be randomly assigned to one of two treatment arms:

A) atezolizumab+lurbinectedin or B) atezolizumab. Randomization will occur in a 1:1 ratio through use of a permuted-block randomization method to ensure a balanced assignment to each treatment arm. Randomization will be stratified by:

- ECOG PS at maintenance baseline (0 vs. 1)
- LDH at maintenance baseline ( $\leq$  ULN vs  $>$  ULN) via local laboratory test
- Presence of liver metastases at induction baseline (yes vs. no)
- Prior receipt of PCI (yes vs. no)

Although this is an open-label study, the randomized treatment assignments from the IxRS will be withheld from members of the Sponsor, including, but not limited to, the study's Medical Monitor, Study Statistician, Statistical Programmer, and Study Data Manager. Members of the Sponsor are not permitted to perform analyses or summaries by randomized treatment assignment and/or actual treatment received before the randomized treatment assignments are disclosed to the study team for the pre-specified analysis.

## **6.4 STUDY TREATMENT COMPLIANCE**

When participants are dosed at the site, they will receive study treatment directly from the investigator or designee, under medical supervision. The dose of study treatment and the study participant's identification will be confirmed at the time of dosing by a member of the study site staff other than the person administering the study treatment.

Details on treatment administration (e.g., dose and timing) should be noted in the source documents and on the Study Drug Administration electronic Case Report Form (eCRF). Cases of accidental overdose or medication error, along with any associated adverse events, should be reported as described in [Appendix 3](#).

## **6.5 DOSE MODIFICATION**

Up to 2 lorbinecetin dose reductions are allowed (first dose reduction: 2.6 mg/m^2 Q3W; second dose reduction: 2 mg/m^2 Q3W). Once the dose has been reduced for an individual participant, it must not be re-escalated again. If the participant receives a lorbinecetin dose of 2 mg/m^2 and experiences a toxicity that would warrant a lorbinecetin dose reduction, treatment with lorbinecetin must be permanently discontinued (refer to [Table A6-1](#) for more details on dose modification guidelines for lorbinecetin).

Modification of the atezolizumab dose is not permitted.

If study treatment has to be temporarily interrupted or permanently discontinued to manage toxicity, atezolizumab and lorbinecetin can be interrupted or discontinued independently from each other (i.e., an interruption or discontinuation of lorbinecetin does not necessarily result in a simultaneous interruption or discontinuation of atezolizumab; an interruption or discontinuation of atezolizumab does not necessarily result in a simultaneous interruption or discontinuation of lorbinecetin), depending on the toxicity and suspected causality (see [Appendix 6](#) for management guidelines). Should one study drug be temporarily interrupted because of toxicity caused by lorbinecetin or atezolizumab, treatment will be restarted such that the administration of both study drugs remains synchronized.

## **6.6 CONTINUED ACCESS TO STUDY TREATMENT AFTER THE END OF THE STUDY**

The Sponsor will offer continued access to atezolizumab free of charge to eligible participants in accordance with the Roche Global Policy on Continued Access to Investigational Medicinal Product, as outlined below. The Sponsor will evaluate whether to continue providing lorbinecetin in accordance with this policy.

A participant will be eligible to receive atezolizumab and/or lorbinecetin after completing the study if all of the following conditions are met:

- The participant has a life-threatening or severe medical condition and requires continued treatment with atezolizumab and/or lorbinecetin for his or her well-being.
- There are no appropriate alternative treatments available to the participant.
- The participant and his or her doctor comply with and satisfy any legal or regulatory requirements that apply to them.

A participant will not be eligible to receive atezolizumab and/or lorbinecetin after completing the study if any of the following conditions are met:

- Atezolizumab and/or lorbinecetin are commercially marketed in the participant's country and are reasonably accessible to the participant (e.g., is covered by the participant's insurance or wouldn't otherwise create a financial hardship for the participant).

- The Sponsor has discontinued development of atezolizumab and/or lorbinecetin or data suggest that the treatment is not effective for ES-SCLC.
- The Sponsor has reasonable safety concerns regarding atezolizumab and/or lorbinecetin as a treatment for ES-SCLC.
- Provision of atezolizumab and/or lorbinecetin is not permitted under the laws and regulations of the participant's country.

The Roche Global Policy on Continued Access to Investigational Medicinal Product is available at the following website:

[https://assets.roche.com/f/176343/x/1b18e080e0/2025-revision-roche\\_global\\_policy\\_on\\_continued\\_access\\_to\\_investigational\\_interventions.pdf](https://assets.roche.com/f/176343/x/1b18e080e0/2025-revision-roche_global_policy_on_continued_access_to_investigational_interventions.pdf)

## 6.7 TREATMENT OF OVERDOSE

An overdose is the administration of a drug in a quantity that is higher than the assigned dose. There is no known antidote for treating an overdose. Cases of overdose, along with any associated adverse events, should be reported as described in [Appendix 3](#).

In the event of an overdose, the investigator should take the following steps:

1. Contact the Medical Monitor immediately.
2. Closely monitor the participant for any adverse event or serious adverse event and laboratory abnormalities.

## 6.8 CONCOMITANT THERAPY

Any medication and/or vaccine, including over-the-counter or prescription medicines, vitamins, and/or herbal supplements used by a participant in addition to protocol-mandated treatment from 7 days prior to enrollment until the treatment discontinuation visit must be recorded on the Concomitant Medications eCRF along with the following information:

- Reason for use (indication)
- Dates of administration, including start and end dates
- Dosage information, including dose and frequency

For participants who discontinue study treatment for any reason other than disease progression, information on the administration of any COVID-19 vaccine will continue to be collected beyond the treatment discontinuation visit until radiographic disease progression per RECIST v1.1 has been confirmed. This is due to the risk of lymphadenopathy as a result of a COVID-19 vaccine (see the respective information in [Appendix 8](#)).

The Medical Monitor may be consulted if there are any questions related to concomitant or prior therapy.

### **6.8.1 Permitted Therapy**

Participants are permitted to use the following therapies during the study:

- Oral contraceptives with a failure rate of <1% per year (see Section 5.1)
- Hormone replacement therapy
- Prophylactic or therapeutic anticoagulation therapy (such as warfarin at a stable dose or low-molecular-weight heparin)
- Vaccines (such as influenza, COVID-19)
  - Live attenuated vaccines are not permitted (see Section 6.8.3)
- Megestrol acetate administered as an appetite stimulant
- Mineralocorticoids (e.g., fludrocortisone)
  - Inhaled or low-dose corticosteroids administered for COPD or asthma
- Low-dose corticosteroids administered for orthostatic hypotension or adrenocortical insufficiency
- PCI administered after completion of induction treatment, per local standard of care; requirement to complete PCI before randomization into the maintenance phase
- Palliative radiotherapy (e.g., treatment of known bone metastases or symptomatic relief of pain):
  - Treatment with lorbrena must be withheld during palliative radiotherapy and lorbrena must not be restarted less than 2 weeks following the last dose of radiotherapy
  - Treatment with atezolizumab may be continued during palliative radiotherapy
- Blood products and transfusions, as clinically indicated
- Bisphosphonates
- Erythropoietin use according to local guidelines
- G-CSF
- In case of nausea or vomiting, prophylaxis and/or symptomatic treatment for emesis according to local guidelines

Premedication with antihistamines, anti-pyretics, and/or analgesics may be administered for the second and subsequent atezolizumab infusions only, at the discretion of the investigator.

In general, investigators should manage a participant's care (including preexisting conditions) with supportive therapies other than those defined as cautionary or prohibited therapies (see Section 6.8.2 and Section 6.8.3) as clinically indicated, per local standard practice. Participants who experience infusion-associated symptoms may be treated symptomatically with acetaminophen, ibuprofen, diphenhydramine, and/or H2-receptor antagonists (e.g., famotidine, cimetidine), or equivalent medications per local standard practice. Serious infusion-associated events manifested by dyspnea,

hypotension, wheezing, bronchospasm, tachycardia, reduced oxygen saturation, or respiratory distress should be managed with supportive therapies as clinically indicated (e.g., supplemental oxygen and  $\beta_2$ -adrenergic agonists; see [Appendix 6](#)).

### **6.8.2 Cautionary Therapy**

#### **6.8.2.1 Cautionary Therapy for Atezolizumab-Treated Participants Corticosteroids, Immunosuppressive Medications, and TNF- $\alpha$ Inhibitors**

Systemic corticosteroids, immunosuppressive medications, and TNF- $\alpha$  inhibitors may attenuate potential beneficial immunologic effects of treatment with atezolizumab. Therefore, in situations in which systemic corticosteroids, immunosuppressive medications, or TNF- $\alpha$  inhibitors would be routinely administered, alternatives, including antihistamines, should be considered. If the alternatives are not feasible, systemic corticosteroids, immunosuppressive medications, and TNF- $\alpha$  inhibitors may be administered at the discretion of the investigator.

Systemic corticosteroids or immunosuppressive medications are recommended, at the discretion of the investigator, for the treatment of specific adverse events when associated with atezolizumab therapy (see [Appendix 6](#) for details).

#### **6.8.2.2 Medications Given with Precaution due to Effects Related to CYP Enzymes**

In vitro studies with human liver microsomes have shown that CYP3A4 is a major metabolic enzyme involved in the metabolism of lurbinectedin, followed by CYP2E1, CYP2D6, and CYP2C9. The contribution of other CYP isoenzymes is negligible. Thus, concomitant medications which induce or inhibit CYP3A4 should be carefully monitored or avoided, whenever possible (see [Appendix 16](#)). A significant interaction with aprepitant (CYP3A4 inhibitor) is suggested by Phase II data with lurbinectedin from participants with ovarian cancer and a Phase II Study PM1183-A-008-13 in participants with advanced solid tumors where lurbinectedin clearance was reduced by approximately 42% in the presence of aprepitant and participants experienced unusually long-lasting neutropenia, as well as thrombocytopenia. Although all participants recovered from these events, the use of aprepitant and equivalent agents (e.g., fosaprepitant) is not permitted.

Based on in vitro studies, lurbinectedin was shown to inhibit CYP2C8, CYP3A4 and CYP2B6. However, according to guidelines from the European Medicines Agency and FDA, the calculated in vivo impact of lurbinectedin on those CYP isoenzymes was insignificant. Therefore, no potential drug-drug interaction is expected between lurbinectedin and drugs which are metabolized by CYP3A4, CYP2C8, or CYP2B6 (see [Appendix 16](#)).

The investigator should consult the prescribing information and Investigator's Brochures when determining whether a concomitant medication can be safely administered with study treatment. In addition, the investigator should contact the Medical Monitor if questions arise regarding medications not listed above.

#### **6.8.2.3      Herbal Therapies**

Concomitant use of herbal therapies is not recommended because their pharmacokinetics, safety profiles, and potential drug–drug interactions are generally unknown. However, herbal therapies not intended for the treatment of cancer (see Section 6.8.3) may be used during the study at the discretion of the investigator.

#### **6.8.3      Prohibited Therapy**

Use of the following concomitant therapies is prohibited as described below:

- Concomitant therapy intended for the treatment of cancer (including, but not limited to, chemotherapy, hormonal therapy, immunotherapy, radiotherapy, and herbal therapy), whether health authority–approved or experimental, is prohibited for various time periods prior to starting study treatment, depending on the agent (see Section 6.8.2), and during study treatment, until disease progression is documented and the participant has discontinued study treatment, with the exception of palliative radiotherapy and local therapy under certain circumstances
- Cisplatin instead of carboplatin in the induction phase
- Investigational therapy is prohibited within 28 days prior to enrollment and during study treatment
- Live, attenuated vaccines (e.g., FluMist®) are prohibited within 4 weeks prior to enrollment, during study treatment, and for 5 months after the final dose of atezolizumab or for 2 weeks after the final dose of lurbinectedin, whichever is later
- Systemic immunostimulatory agents (including, but not limited to, interferons and IL-2) are prohibited within 4 weeks or 5 drug-elimination half-lives (whichever is longer) prior to enrollment and during study treatment because these agents could potentially increase the risk for autoimmune conditions when given in combination with study treatment
- Systemic immunosuppressive medications other than corticosteroids as described in Section 6.8.2.1 (including, but not limited to, cyclophosphamide, azathioprine, methotrexate, and thalidomide) are prohibited during study treatment because these agents could potentially alter the efficacy and safety of study treatment
- Radiotherapy other than limited-field radiotherapy for pain control
- Aprepitant or other neurokinin-1 receptor (NK-1) antagonists (e.g., fosaprepitant) for participants receiving treatment with lurbinectedin

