## 7.1 DISCONTINUATION OF STUDY TREATMENT

It may be necessary for a participant to permanently discontinue (definitive discontinuation) study treatment. If study treatment is definitively discontinued, the participant will remain in the study follow-up phase. See the schedule of activities (see Section 1.3, [Table 2](#)) for data to be collected at the time of discontinuation of study treatment and for any further follow-up evaluations that need to be completed.

Participants must permanently discontinue study treatment if any of the following criteria are met:

- Any medical condition that the investigator determines may jeopardize the participant's safety if *the participant* continues to receive study treatment
- Investigator determination that treatment discontinuation is in the best interest of the participant
- Pregnancy
- Disease progression per RECIST v1.1
- Loss of clinical benefit as determined by the investigator after an integrated assessment of radiographic and biochemical data, local biopsy results (if available), and clinical status (e.g., symptomatic deterioration such as pain secondary to disease)
- Use of any anti-cancer therapy not allowed per protocol or use of a prohibited therapy (see Section [6.8.3](#))
- Intolerable toxicity related to study treatment, including development of an immune-mediated adverse event determined by the investigator to be unacceptable given the individual participant's potential response to therapy and severity of the event

The primary reason for study treatment discontinuation must be documented on the appropriate eCRF.

Participants will return to the clinic for a treatment discontinuation visit within 30 days after the final dose of study drug or within 30 days from the date the decision was made to permanently discontinue study treatment.

See the schedule of activities in Section 1.3 ([Table 2](#)) for details on follow-up assessments to be performed for participants who permanently discontinue study treatment. If a participant requests to be withdrawn from study treatment and/or follow-up, this request must be documented in the source documents and signed by the investigator.

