### **A6–2.4.2 Guidelines for Management of Adverse Events Associated with Atezolizumab**

Toxicities associated or possibly associated with atezolizumab treatment should be managed according to standard medical practice. Additional tests, such as autoimmune serology or biopsies, should be used to evaluate for a possible immunogenic etiology, when clinically indicated.

Although toxicities observed with atezolizumab have been mild and self-limiting, they should be recognized early and treated promptly to avoid potential major complications. Discontinuation of atezolizumab may not have an immediate therapeutic effect, and in severe cases, immune-mediated toxicities may require acute management with topical corticosteroids, systemic corticosteroids, or other immunosuppressive agents.

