##### **Use of Corticosteroids and Immunosuppressants for Managing Adverse Events:**

In the guidance for specific events below, treatment with high-dose corticosteroids refers to 1–2 mg/kg/day oral prednisone (or equivalent) or IV methylprednisolone (or equivalent), and an additional immunosuppressive agent can be added if symptoms do not improve within 48 hours after initiating high-dose corticosteroids. If corticosteroids have been initiated, they must be tapered over  $\geq 1$  month to the equivalent of  $\leq 10$  mg/day of oral prednisone before atezolizumab can be resumed.

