## Appendix 6: Safety Plan: Management of Identified and Potential Risks

Action to be Taken with Atezolizumab: Treatment with atezolizumab may be withheld or permanently discontinued because of toxicities, as specified below. If atezolizumab is withheld, treatment can be resumed if the event resolves to Grade 1 or better, or when symptoms improve as specified below. As a general rule, atezolizumab can be withheld for up to 12 weeks after event onset. Treatment with atezolizumab may be resumed if the event improves to Grade ≤1 within 12 weeks and if corticosteroids have been reduced to ≤10 mg/day oral prednisone or equivalent within 12 weeks. If atezolizumab is withheld for >12 weeks (or 4 cycles) of initiating steroids, the participant will be discontinued from atezolizumab. If an event does not resolve to Grade 1 or better while withholding atezolizumab, permanently discontinue atezolizumab and contact the Medical Monitor. Resumption of atezolizumab may be considered in patients who are deriving benefit and have fully recovered from an immune-mediated event, except when resumption of atezolizumab is expressly prohibited as described below. The decision to rechallenge patients with atezolizumab should be based on the investigator's benefit-risk assessment and should be documented by the investigator. The Medical Monitor is available to advise as needed.			
Event	Symptoms or CTCAE Severity Grade	Action to be Taken with Atezolizumab	Adverse Event Management [To Be Implemented in Combination with Above General Guidance]
Pulmonary event	Grade 1	
 
Continue with one exception: For pneumonitis, consider withholding and resuming on radiographic evidence of improvement.
 
	
 
Re-evaluate on serial imaging.
 
Closely monitor patients, including asymptomatic patients.
 

	Grade 2	
 
Withhold.
 
	
 
Consider bronchoscopy or BAL with or without transbronchial biopsy.
 
Initiate treatment with high-dose oral corticosteroids.
 

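### Section 6.8.3 bans non-steroid systemic immunosuppressants and Section 7.1 makes their use a permanent stop, yet Section 6.8.2.1 and Table A6-5 allow them; rolapitant is also treated in two ways

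*Protocol*

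**What the plan says.** The ban is in Protocol Section 6.8.3: "Systemic immunosuppressive medications other than corticosteroids as described in Section 6.8.2.1 (including, but not limited to, cyclophosphamide, azathioprine, methotrexate, and thalidomide) are prohibited" for the duration of study treatment.

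The consequence is in Section 7.1. The list opens "Participants must permanently discontinue study treatment if any of the following criteria are met", and one item is "Use of any anti-cancer therapy not allowed per protocol or use of a prohibited therapy", with a pointer back to Section 6.8.3.

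Other passages take a different line on the same class of drug:

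- Section 6.8.2.1: "If the alternatives are not feasible, systemic corticosteroids, immunosuppressive medications" and TNF-α inhibitors are left to the investigator's judgment. The same section adds "Systemic corticosteroids or immunosuppressive medications are recommended, at the discretion of the investigator, for the treatment of specific adverse events" linked to atezolizumab.
- Section A6-2.4.2: "in severe cases, immune-mediated toxicities may require acute management with topical corticosteroids, systemic corticosteroids, or other immunosuppressive agents".
- Table A6-5, general guidance on corticosteroids and immunosuppressants: "an additional immunosuppressive agent can be added if symptoms do not improve within 48 hours after initiating high-dose corticosteroids".
- Table A6-5, general guidance on atezolizumab: "If atezolizumab is withheld, treatment can be resumed if the event resolves to Grade 1 or better". It also lets resumption be considered after full recovery from an immune-mediated event, unless the row expressly rules that out.

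On NK-1 antagonists, Section 6.8.3 bars aprepitant and all others of the class for participants receiving lurbinectedin. Section A6-2.4.1.3 repeats the bar but excepts rolapitant.

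**The concern.** A site that follows the toxicity guidance can give a drug that another section treats as grounds for ending study treatment for good. One section then lets the participant go back on atezolizumab while another requires a permanent stop. Two sites facing the same event could act differently, and each could point to protocol text in support.

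The consequences are for conduct and recording. SAP Section 4.6.1 summarizes reasons for treatment discontinuation and major protocol deviations by arm. If one site records a mandatory stop and another records permitted toxicity management, those summaries mix two conventions.

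**Working it through.** No sample size, power or alpha figure is involved, so the check sets the passages side by side and counts rows of Table A6-5. A row here is one event at one grade level.

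**1. What is banned.** In Section 6.8.3 the exception is attached to corticosteroids, and the drugs then named as examples of the ban are all non-steroids. Read as written, any other systemic immunosuppressant is prohibited during study treatment.

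**2. What follows from use.** Any one item in the Section 7.1 list is enough, and the prohibited-therapy item has no exemption for managing an adverse event. Section 3 defines study treatment to include both atezolizumab and lurbinectedin, so the stop reaches both. Sections 5, 8 and A1-11 exclude waivers.

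**3. Rows that only withhold atezolizumab but suggest adding an immunosuppressive agent.**

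| Row | Atezolizumab action | Agent suggested |
|---|---|---|
| Diarrhea or colitis, Grade 2 | Withhold | Yes, if no improvement |
| Myositis, Grade 2 | Withhold | Yes, if no improvement |
| Myositis, Grade 3 | Withhold; permanent stop only if not resolved to Grade 1 or better | Yes, if no improvement in 24–48 hours |

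Count: 1 + 1 + 1 = 3. This is a minimum. In the text available, the management cells for colitis Grades 3 and 4 may be a single merged cell; if so, colitis Grade 3 is a fourth row. The general 48-hour guidance also reaches other withhold rows that use high-dose corticosteroids, such as pulmonary Grade 2 and renal Grade 2; these are not counted.

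**4. Rows that permanently discontinue atezolizumab and suggest such an agent, without a full ban on resumption.** Four print no ban: hepatic Grade 3–4 (without hepatocellular carcinoma), colitis Grade 4, pancreatitis Grade 4 and renal Grade 3–4. In a fifth, the most severe pulmonary row, the ban covers pneumonitis only. Count: 4 + 1 = 5. Here the conflict can arise in two ways. Sections A6-2.1 and A6-2.2 allow lurbinectedin to continue alone after atezolizumab is stopped for a severe immune-related event, and the general guidance leaves atezolizumab rechallenge open after full recovery.

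**5. One participant traced through.** Suppose Grade 2 colitis does not improve on corticosteroids and an immunosuppressive agent is added.

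- Table A6-5: atezolizumab is withheld and can be resumed once the event resolves and corticosteroids have been tapered as required.
- Sections 6.8.3 and 7.1: use of the agent ends all study treatment permanently.

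Both outcomes come from current Version 8 text.

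**6. NK-1 antagonists.** The mismatch is one drug. Even if the parenthesis in Section A6-2.4.1.3 qualifies only the related Substance P antagonists, that section contains a rolapitant exception and Section 6.8.3 has none.

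**The case against.** The best counter-argument is that Section 6.8.3 was meant to exempt everything Section 6.8.2.1 covers. It cites that section, whose heading includes immunosuppressive medications and TNF-α inhibitors as well as corticosteroids. The induction exclusion criterion in Section 5.2.1 lists the same example drugs plus corticosteroids and anti-TNF-α agents; Section 6.8.3 names neither of these among its banned examples, and both are handled by name in Section 6.8.2.1. Nor would this reading empty the ban completely, since Section 6.8.2.1 applies where alternatives are not feasible or a specific atezolizumab-associated event is treated. That may well be the intent, but it is not written: the cross-reference follows corticosteroids, the list of examples is open-ended, and a site applying the text literally reaches the stop.

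Other objections have some weight:

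- Table A6-5 is permissive. It suggests agents and allows resumption but compels neither, so the conflict arises only once an agent is given. This is correct, and it limits the scope. It does not help the participant who has been given one.
- The 5 permanent-discontinuation rows need a chain of events, and another stop may already apply, such as the liver criteria in Section 7.1.1. These rows are therefore secondary; the 3 withhold rows carry the point.
- A site that never gives rolapitant complies with both NK-1 passages. That mismatch is small and adds nothing to the main point.
- The statistical consequence is nil and the OS cutoff has passed. This is accepted. However, Version 8 revised the atezolizumab management guidelines and extended the expected study length to approximately 90 months, so the treatment rules still apply to anyone on treatment.

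**Conclusion.** The inconsistency is real as written and should be fixed. It is direct in at least 3 rows of Table A6-5 and conditional in 5 more, with one further drug, rolapitant, treated in two ways.

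The conclusion rests on the literal reading of the exception in Section 6.8.3 and arises only when a non-steroid systemic immunosuppressant is actually given. The documents give neither the rate of such use nor the number of participants still on treatment, so no participant count is offered.

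Type I error and power are unaffected. The primary estimands handle early discontinuation by a treatment policy strategy, so they are unaffected too. What remains is whether treatment continues for an individual participant, and how discontinuation reasons and deviations are recorded.

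**What to change.** Reconcile Sections 6.8.2.1, 6.8.3, 7.1, A6-2.4.1.3, A6-2.4.2 and Table A6-5 so that each agent has one status, and so that the consequence of its use is stated once for atezolizumab and once for lurbinectedin. Section 7.1 should say explicitly whether its prohibited-therapy criterion applies to drugs given to manage an adverse event. The sponsor's clinical team must decide which statement stands; this review takes no position on that.

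The cost is protocol wording, or a clarification letter to sites until the next amendment. No new data or participants are needed.
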